1.1 Does the protocol specify timelines for				
1.1.1 Start of data collection ¹				7
1.1.2 End of data collection ²				7
1.1.3 Study progress report(s)				
1.1.4 Interim progress report(s)				
1.1.5 Registration in the EU PAS register				Pg. no. 1
1.1.6 Final report of study results.				7

Comments:

1.1.5 EU PAS registration completed and number added in the title page.

Section 2: Research question	Yes	No	N/A	Section Number
2.1 Does the formulation of the research question and objectives clearly explain:				
2.1.1 Why the study is conducted? (e.g. to address an important public health concern, a risk identified in the risk management plan, an emerging safety issue)				8
2.1.2 The objective(s) of the study?				9
2.1.3 The target population? (i.e. population or subgroup to whom the study results are intended to be generalised)				10.1.2
2.1.4 Which hypothesis(-es) is (are) to be tested?				
2.1.5 If applicable, that there is no a priori hypothesis?				

Comments:

2.1.4.- No formal hypothesis is being tested in the PMS study

2.1.5.- No formal hypothesis is being tested in the PMS study

Section 3: Study design	Yes	No	N/A	Section Number
3.1 Is the study design described? (e.g. cohort, case-control, cross-sectional, new or alternative design)				10.1
3.2 Does the protocol specify whether the study is based on primary, secondary or combined data collection?				10.2.2

¹ Date from which information on the first study is first recorded in the study dataset or, in the case of secondary use of data, the date from which data extraction starts.

² Date from which the analytical dataset is completely available.

Section 3: Study design	Yes	No	N/A	Section Number
3.3 Does the protocol specify measures of occurrence? (e.g. incidence rate, absolute risk)				
3.4 Does the protocol specify measure(s) of association? (e.g. relative risk, odds ratio, excess risk, incidence rate ratio, hazard ratio, number needed to harm (NNH) per year)				10.6.1
3.5 Does the protocol describe the approach for the collection and reporting of adverse events/adverse reactions? (e.g. adverse events that will not be collected in case of primary data collection)				12

Comments:

3.3.- This is not applicable in case of a NIS study on PraxbindTM with no defined incidence rate for this study.

Section 4: Source and study populations	Yes	No	N/A	Section Number
4.1 Is the source population described?				10.1.2
4.2 Is the planned study population defined in terms of: 
 4.2.1 Study time period? 4.2.2 Age and sex? 4.2.3 Country of origin? 4.2.4 Disease/indication? 4.2.5 Duration of follow-up? 	    	    	    	10.2 10.2
4.3 Does the protocol define how the study population will be sampled from the source population? (e.g. event or inclusion/exclusion criteria)				10.1.2

Comments:

Section 5: Exposure definition and measurement	Yes	No	N/A	Section Number
5.1 Does the protocol describe how the study exposure is defined and measured? (e.g. operational details for defining and categorising exposure, measurement of dose and duration of drug exposure)				10.2
5.2 Does the protocol address the validity of the exposure measurement? (e.g. precision, accuracy, use of validation sub-study)				
5.3 Is exposure classified according to time windows? (e.g. current user, former user, non-use)				
5.4 Is exposure classified based on biological mechanism of action and taking into account the pharmacokinetics and pharmacodynamics of the drug?				

Comments:

Praxbind™ is administered as a total dose (5g) across two separate vials of 2.5g each one after the other immediately.

Section 6: Outcome definition and measurement	Yes	No	N/A	Section Number
6.1 Does the protocol specify the primary and secondary (if applicable) outcome(s) to be investigated?				10.2.2
6.2 Does the protocol describe how the outcomes are defined and measured?				10.2.2
6.3 Does the protocol address the validity of outcome measurement? (e.g. precision, accuracy, sensitivity, specificity, positive predictive value, prospective or retrospective ascertainment, use of validation sub-study)				
6.4 Does the protocol describe specific endpoints relevant for Health Technology Assessment? (e.g. HRQoL, QALYs, DALYs, health care services utilisation, burden of disease, disease management)				

Comments:

Section 7: Bias	Yes	No	N/A	Section Number
7.1 Does the protocol describe how confounding will be addressed in the study?				
7.1.1. Does the protocol address confounding by indication if applicable?				
7.2 Does the protocol address:				
7.2.1. Selection biases (e.g. healthy user bias)				
7.2.2. Information biases (e.g. misclassification of exposure and endpoints, time-related bias)				
7.3 Does the protocol address the validity of the study covariates?				

Comments:

Since there is no comparator arm in the study and only one standard dose of study drug is studied, there are no confounding variables. Hence, the entire section is not applicable.

Section 8: Effect modification	Yes	No	N/A	Section Number
8.1 Does the protocol address effect modifiers? (e.g. collection of data on known effect modifiers, sub-group analyses, anticipated direction of effect)				

Comments:

This is an India only study and hence there will be no sub-group analysis done for this study.

Section 9: Data sources	Yes	No	N/A	Section Number
9.1 Does the protocol describe the data source(s) used in the study for the ascertainment of:				
9.1.1 Exposure? (e.g. pharmacy dispensing, general practice prescribing, claims data, self-report, face-to-face interview, etc.)				10.3
9.1.2 Outcomes? (e.g. clinical records, laboratory markers or values, claims data, self-report, patient interview including scales and questionnaires, vital statistics, etc.)				10.3
9.1.3 Covariates?				
9.2 Does the protocol describe the information available from the data source(s) on:				
8.2.1 Exposure? (e.g. date of dispensing, drug quantity, dose, number of days of supply prescription, daily dosage, prescriber)				10.2.1
8.2.2 Outcomes? (e.g. date of occurrence, multiple event, severity measures related to event)				10.2.2
8.2.3 Covariates? (e.g. age, sex, clinical and drug use history, co-morbidity, co-medications, life style, etc.)				10.2.3
9.3 Is a coding system described for:				
9.3.3 Exposure? (e.g. WHO Drug Dictionary, Anatomical Therapeutic Chemical (ATC)Classification System)				
9.3.2 Outcomes? (e.g. International Classification of Diseases (ICD)-10, Medical Dictionary for Regulatory Activities (MedDRA))				
9.3.3 Covariates?				
9.4 Is a linkage method between data sources described? (e.g. based on a unique identifier or other)				

Comments:

9.3.- The coding system will be a part of the Data Analysis plan.

Section 10: Analysis plan	Yes	No	N/A	Section Number
10.1 Is the choice of statistical techniques described?				10.6.1
10.2 Are descriptive analyses included?				10.6.1
10.3 Are stratified analyses included?				
10.4 Does the plan describe methods for adjusting for confounding?				
10.5 Does the plan describe methods for handling missing data?				
10.6 Is sample size and/or statistical power estimated?				10.4

Comments:

Section 11: Data management and quality control	Yes	No	N/A	Section Number
11.1 Does the protocol provide information on data storage? (e.g. software and IT environment, database maintenance and anti-fraud protection, archiving)				10.9.2.2.1
11.2 Are methods of quality assurance described?				10.9.1
11.3 Is there a system in place for independent review of study results?				

Comments:

Section 12: Limitations	Yes	No	N/A	Section Number
12.1 Does the protocol discuss the impact on the study results of: 12.1.1 Selection bias? 12.1.2 Information bias? 12.1.3 Residual/unmeasured confounding? (e.g. anticipated direction and magnitude of such biases, validation sub-study, use of validation and external data, analytical methods)	  	  	  	10.9 10.9
12.2 Does the protocol discuss study feasibility? (e.g. study size, anticipated exposure, duration of follow-up in a cohort study, patient recruitment)				10.4

Comments:

Section 13: Ethical issues	Yes	No	N/A	Section Number
13.1 Have requirements of Ethics Committee/ Institutional Review Board been described?				11.1
13.2 Has any outcome of an ethical review procedure been addressed?				11.1
13.3 Have data protection requirements been described?				11.1

Comments:

Section 14: Amendments and deviations	Yes	No	N/A	Section Number
14.1 Does the protocol include a section to document amendments and deviations?				6

Comments:

Proprietary confidential information © 2018 Boehringer Ingelheim International GmbH or one or more of its affiliated companies

Section 15: Plans for communication of study results	Yes	No	N/A	Section Number
15.1 Are plans described for communicating study results (e.g. to regulatory authorities)?				12
15.2 Are plans described for disseminating study results externally, including publication?				12

Comments:

### **3 LIST OF ABBREVIATIONS**

Term	Definition / description
AE	Adverse Event
CTC	Common Terminology Criteria
CTP	Clinical Trial Protocol
EDC	Electronic Data Capture
ICH	International Conference On Harmonisation
MedDRA	Medical Dictionary For Regulatory Activities
MQRM	Medical Quality Review Meeting
PT	Preferred Term
PV	Protocol Violation
Q1	Lower Quartile
Q3	Upper Quartile
SA	Statistical Analysis
SD	Standard Deviation
SOC	System Organ Class
ToC	Table of contents
TSAP	Trial Statistical Analysis Plan

## **4 INTRODUCTION**

“As per ICH E9, the purpose of this document is to provide a more technical and detailed elaboration of the principal features of the analysis described in the protocol, and to include detailed procedures for executing the statistical analysis of the primary and secondary variables and other data.

This TSAP assumes familiarity with the Clinical Trial Protocol (CTP)version 3.0, dated 13 Sep 2017 and Case Report Form (CRF) Final version 3.0, dated 11 Apr 2018 In particular, the TSAP is based on the planned analysis specification as written in CTP Section 10.6 “Data Analysis”. Therefore, TSAP readers may consult the CTP for more background information on the study, e.g., on study objectives, study design and population, treatments, definition of measurements and variables, planning of sample size.”

SAS® Version 9.2 or higher will be used for all analyses.

The aim of this drug administration surveillance program is to capture a large proportion of the patients treated with Praxbind™ in order to collect data on Praxbind™ prescription patterns in a clinical practice setting in India, with special focus on ADRs and fatal AEs.

## **5 CHANGES IN THE PLANNED ANALYSIS OF THE STUDY**

No changes made in the planned analysis of the study mentioned in the protocol version 3.0, dated 13 Sep 2017.

## **6 OUTCOMES**

### **6.1 PRIMARY OUTCOMES**

- Any suspected ADRs and fatal AEs; with special focus on hypersensitivity and thrombotic event, occurred within 7 days after Praxbind™ administration.

### **6.2 SECONDARY OUTCOMES**

#### **6.2.1 Secondary outcome**

- Percentage of patients who either received Praxbind™ for emergency surgery/urgent procedures or in life-threatening or uncontrolled bleeding at the end of 2 years.

#### **6.2.2 Key secondary outcome**

- This section is not applicable as no key secondary outcome has been specified in the protocol.

## **6.4 OTHER VARIABLES**

In this study, the following variables will be considered.

#### **➤ Site characteristics:**

To evaluate the diversity of sites the following information will be collected for each participating site:

- Multi-specialty hospitals with emergency management facilities and having access to Praxbind™
- Practice type (academic, non-academic, private, Government)
- Availability of prescription/medical records at the site.

➤ **Patient Data:**

- Year of Birth
- Gender: Male or Female
- Vital Signs
- Physical Examination
- Laboratory data (Data would be collected of lab results performed as a routine practice.  
No additional lab tests should be performed specifically for this study purpose)
- Pregnancy status in case of female patient

➤ **Medical History:**

- Name, dose and last intake of previous anticoagulant medications (Dabigatran);
- Pertaining to haemorrhagic risk factors or impact on safety outcomes (e.g. renal impairment, congenital or acquired coagulation disorders, thrombocytopenia or functional platelet defects, recent biopsy, recent surgery, major trauma, bacterial endocarditis, esophagitis, gastritis, gastroesophageal reflux, hepatic disorders, vascular disorders, neoplasms/cancer, inherited vascular disorder (aneurysms, arteriovenous malformation, microangiopathy) and the HAS-BLED score).
- Concomitant treatment pertaining to haemorrhagic risk factors or impact on safety outcomes (e.g. acetylsalicylic acid, non-steroidal anti-inflammatory drugs, clopidogrel, selective serotonin reuptake inhibitors or serotonin-norepinephrine reuptake inhibitors, Strong P-Gp inhibitors (e.g. Ketoconazol, Clarithromycin, ticagrelor), chemotherapy, radiation therapy).

➤ **Praxbind™ utilization:**

- Department (emergency, operating room, ICU, other patient setting);
- Type of surgery /procedure if applicable;
- Information on bleeding event including location (Gastrointestinal tract; Intracranial; Skin, Urogenital tract, Intramuscular, Retroperitoneal, Undefined location, otherdefined location) if applicable, and if bleeding was life-threatening (yes/no);

- Indication: life-threatening or uncontrolled bleeding requiring urgent medical intervention, emergency surgery or other urgent medical procedure necessitating rapid reversal of the anticoagulant effect of dabigatran prior to surgery/procedure, scheduled or planned surgery/procedure, other.
- Dosage and administration (total dose administered and time interval between the administration of the two vials; vials to be taken one after the other, immediate administration of the second vial is mandatory);
- Premature PraxbindTM administration discontinuation (yes/no).
- In case if the patient requires an additional 5 g dose for the following conditions as per the label:
  - i. recurrence of clinically relevant bleeding together with prolonged clotting times, or
  - ii. if potential re-bleeding would be life-threatening and prolonged clotting times are observed, or
  - iii. patients require a second emergency surgery/urgent procedure and have prolonged clotting times.
- Information on restart of anticoagulation therapy (which anticoagulation treatment including dose and when was it restarted).
- All adverse drug reactions (ADRs, serious and non-serious) associated with PraxbindTM.
- All AEs with fatal outcome in patients exposed to PraxbindTM.

## **7 GENERAL ANALYSIS DEFINITIONS**

### **7.1 TREATMENT**

This is a post marketing surveillance study wherein patients will be eligible for the study if they are prescribed Praxbind as per the approved label. The drug administration surveillance program is designed as a multi-center program enrolling patients administered with Praxbind. Data will be collected for patients who have been treated with Praxbind within 2 years. There are no protocol mandated follow-up visits or procedures associated with the program. No interference with usual medical care is involved, and thus it will not affect the treatment of patients.

### **7.2 IMPORTANT PROTOCOL VIOLATIONS**

This surveillance is mainly focused on prescription patterns of use of Praxbind in a clinical practice setting, with special focus on ADRs and fatal AEs. So in this surveillance per protocol (PP) analysis will not be considered. Hence, the iPV table will be included for completeness and also to demonstrate a level of quality (or adherence to the protocol).

The following table defines, but is not limited to, the different categories of important PVs:

**Table 6.2: 1 Important Protocol Violation**

Category/ code	Description	Requirements	Detected by	Excluded From;
A	Entrance Criteria Not Met			
A1	Not met criteria for Treatment with Pradaxa and Praxbind™.			
A1.1	Patients not treated with Pradaxa (dabigatran etexilate) capsules or Patients treated with Pradaxa with no requirement of rapid reversal of the anticoagulant effects of dabigatran: 

• For emergency surgery/urgent procedures (or)

• In life-threatening or

	Patients did not receive Pradaxa or patients who received Pradaxa but not required Praxbind™ for reversal of anticoagulant effects of Pradaxa.	Programmatically	None

Category/ code	Description	Requirements	Detected by	Excluded From;
	uncontrolled bleeding			
A2	Inform consent			
A2.1	Written informed consent in accordance with International Conference on Harmonization Good Clinical Practice (GCP) guidelines and local legislation and/or regulations not obtained.	Informed consent not obtained.	Programmatically	None
B	Exclusion criteria met.			
B1	Participation in Other Clinical Trial			
B1.1	Participation in a Praxbind clinical trial.	Patient currently participating or participated previously in other Praxbind clinical trial	Manually	None

**KEY:IPV- Important Protocol Violation**

**Note:** Automated PVs are those detected via an automated programming process using SAS. Manual PVs are those identified during the MQRM or review through patients listings and/or Manual PV log.

Important protocol violations will be defined and documented prior to clinical database lock. A strategy for dealing with data affected by protocol deviations will be agreed upon by the coordinator, Sponsor and Biostatistician before clinical database lock.

When the PV cannot be programmed, the individual patient listings with PV category/code will be generated based on data review and should not be included in the TSAP.

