10.4 STUDY SIZE

This program will be initiated after the commercial availability of PraxbindTM in India. It will include up to 25 patients who require PraxbindTM according to the approved Indian label or the patients included in 2 years at selected Centers approved by the regulatory authority, whichever is earlier.

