10.8 LIMITATIONS OF THE RESEARCH METHODS

This study will include only up to 25 consecutive patients who require PraxbindTM. The data analysis will be done using descriptive statistics with no formal statistical hypothesis.

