The following must be reported by the investigator on the NIS AE form from signing the informed consent onwards until the end of the study:

Type of Report	Timeline
All serious ADRs associated with Praxbind™	immediately within 24 hours
All AEs with fatal outcome in patients exposed to Praxbind™	immediately within 24 hours
All non-serious ADRs associated with Praxbind™	7 calendar days
All pregnancy monitoring forms	7 calendar days

The same timelines apply if follow-up information becomes available for the respective events. In specific occasions the Investigator could inform the Sponsor upfront via telephone. This does not replace the requirement to complete and fax the NIS AE form.

Information required

For each reportable adverse event, the investigator should provide the information requested on the appropriate (e)CRF pages and the NIS AE form.

Reporting of the indication for which Praxbind™ is used

For patients not participating in 1160.189 or 1160.248, the investigator must report the indication for which Praxbind™ is used (emergency surgery/urgent procedures or life-threatening or uncontrolled bleeding) as spontaneous Pradaxa (dabigatran etexilate) case to the above mentioned BI contact for AE/Pregnancy Reporting. For emergency surgery/urgent procedures the underlying condition requiring the surgery/procedure must be indicated in the report.

This reporting obligation is independent of causality assessment, but a causality assessment must always be provided.

Proprietary confidential information © 2018 Boehringer Ingelheim International GmbH or one or more of its affiliated companies

For patients participating in 1160.189 or 1160.248, the reporting of the indication for which Praxbind™ is used must occur within those trials following the requirements for 1160.189 or 1160.248 respectively.

Reporting of related Adverse Events associated with any other BI drug

The investigator is encouraged to report all adverse events related to any BI drug other than Praxbind™ according to the local regulatory requirements for spontaneous AE reporting at the investigator's discretion by using the locally established routes and AE report forms. The term AE includes drug exposure during pregnancy, and, regardless of whether an AE occurred or not, any abuse, off-label use, misuse, medication error, occupational exposure, lack of effect, and unexpected benefit.

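### The SAP says no violation leads to exclusion, yet its Treated Set drops ineligible treated patients and its handling of other affected data stays open until database lock

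*SAP*

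**What the plan says.** SAP 7.2 takes a position against exclusion. It rules out a per-protocol analysis ("So in this surveillance per protocol (PP) analysis will not be considered") and presents the violation table as a record of completeness and quality. All three rows of that table (A1.1, Pradaxa treatment and need for reversal; A2.1, consent; B1.1, participation in a Praxbind trial) show 'None' in the exclusion column.

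The same section then leaves two things open. The list is not closed: "The following table defines, but is not limited to, the different categories of important PVs". The treatment of affected data is put off: "A strategy for dealing with data affected by protocol deviations will be agreed upon by the coordinator, Sponsor and Biostatistician before clinical database lock". Nothing ties that strategy to the 'None' entries, and nothing says that categories added later also carry 'None'.

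SAP 7.3 builds its sets by nesting. The Screened Set is everyone who signed consent, the Entered Set is those of them who met the eligibility criteria, and the Treated Set is those of the Entered Set who received Praxbind. The text and Table 6.3: 1 assign the primary and secondary outcomes to the Treated Set. SAP 8.8 describes the safety population differently, as patients with at least one dose, with no eligibility condition.

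The primary outcome in SAP 6.1 is a safety outcome: "Any suspected ADRs and fatal AEs; with special focus on hypersensitivity and thrombotic event, occurred within 7 days after Praxbind™ administration".

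**The concern.** There are two related problems.

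The first is a contradiction. The violations in the table are failures of the entry criteria. If an eligibility failure removes a patient from the Entered Set, it also removes that patient from the Treated Set and so from the primary outcome. Table 6.2: 1 says the reverse. A programmer following 7.3 and one following 7.2 and 8.8 would count different patients.

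The second is an open decision. Agreeing data handling before lock protects a trial in which those who decide cannot see results by arm. Here no blinding is described and there is no comparator (Protocol Annex 2, checklist section 7: "Since there is no comparator arm in the study and only one standard dose of study drug is studied"). Protocol 12.2 sends events to the sponsor as they occur: "The following must be reported by the investigator on the NIS AE form from signing the informed consent onwards until the end of the study". Serious ADRs and fatal AEs are due within 24 hours and non-serious ADRs within 7 calendar days. The sponsor can therefore know which patients had events when it helps agree the strategy.

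At stake is the headline safety count in a small surveillance study, where one patient more or less is visible in the result.

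**Working it through.** **Step 1. Set the rules side by side for a patient who received Praxbind.**

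| Violation | Table 6.2: 1 | SAP 7.3, read literally | SAP 8.8 |
|---|---|---|---|
| A1.1, entry indication not met | excluded from nothing | not in Entered Set, so not in Treated Set | included |
| B1.1, in a Praxbind trial | excluded from nothing | not in Entered Set, so not in Treated Set | included |
| A2.1, no consent | excluded from nothing | not in Screened Set, so in no set | included, as consent is not mentioned |
| Category added later | not stated | depends on whether it is an eligibility failure | included |

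The three sections cannot all be followed. A1.1 is not an empty row: SAP 6.4 provides indication categories for scheduled or planned surgery and for other reasons, so the plan foresees use outside the two entry indications. B1.1 is detected manually, which under SAP 7.2 means at the quality review meeting or from patient listings or a manual log. SAP 8 puts all study data in the listings.

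**Step 2. Size the effect of losing one patient who had an event.**

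Inputs:
- Size: Protocol 10.4, "It will include up to 25 patients who require PraxbindTM according to the approved Indian label", or fewer if two years of inclusion end first. The documents give no sample-size calculation, so there is no figure of theirs to reproduce.
- Event counts: not given in the documents. One to three events are assumed.
- A smaller study of 10 patients: assumed, to show the effect of low enrolment.
- Interval: exact (Clopper-Pearson) 95%, a choice made here because the SAP names no method.

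For x events in n patients, the rate is x/n. The lower limit is the 2.5% point of Beta(x, n − x + 1), and the upper limit is the 97.5% point of Beta(x + 1, n − x). With x = 0 the lower limit is 0 and the upper limit is 1 − 0.025^(1/n). For n = 24 that is 1 − 0.025^(1/24) = 14.2%.

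| All treated patients | One patient with an event removed |
|---|---|
| 1/25 = 4.0% (0.1 to 20.4) | 0/24 = 0.0% (0 to 14.2) |
| 2/25 = 8.0% (1.0 to 26.0) | 1/24 = 4.2% (0.1 to 21.1) |
| 3/25 = 12.0% (2.5 to 31.2) | 2/24 = 8.3% (1.0 to 27.0) |
| 1/10 = 10.0% (0.3 to 44.5) | 0/9 = 0.0% (0 to 33.6) |
| 2/10 = 20.0% (2.5 to 55.6) | 1/9 = 11.1% (0.3 to 48.2) |

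Removing a patient without an event hardly matters: 1/25 = 4.0% becomes 1/24 = 4.2%. The effect comes from removing a patient who had one.

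**The case against.** The strongest reply is that SAP 7.2 already decides the matter. It plans no per-protocol set, every row reads 'None', and a specific rule should govern a general sentence about strategy. Dealing with affected data may mean no more than flagging, querying or listing. The three rows cover all of the protocol's entry criteria and the study mandates no visits or procedures, so few other kinds of violation are likely. The intervals before and after a removal overlap almost entirely. Protocol 10.8 states that "The data analysis will be done using descriptive statistics with no formal statistical hypothesis", so no error rate is inflated. SAP 8 lists all data, so a removed patient would remain visible.

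Much of this stands. A reader might infer that the sponsor has reserved a right to choose exclusions just before lock, after seeing the events. The documents do not support that. The strategy sentence does not mention exclusion, and its timing is any point before lock, which allows early agreement without requiring it. Nor do the documents show that everyone agreeing the strategy will know the events. Expedited reports go to the sponsor, but nothing says the coordinator or biostatistician sees them, and Protocol 10.3 transfers the CRF data only after the programme closes.

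The reply does not reach SAP 7.3. There, exclusion follows from a fixed definition rather than from discretion, and it contradicts 'None' whatever the strategy turns out to be. Listings do not settle this either, because the reported rate comes from the summary tables.

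**Conclusion.** The point holds and should be corrected. The firmer part is the conflict among SAP 7.2, 7.3 and 8.8: followed literally, 7.3 takes treated patients with an A1.1 or B1.1 violation, and their events, out of the primary safety outcome. The open violation list and unspecified strategy add to it, because they are where the conflict could be settled at a time when the sponsor already knows the serious ADRs and deaths.

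At the cap of 25 patients, one removal can take the observed rate from 4.0% to 0%, or from 8.0% to 4.2%. These figures rest on assumed event counts and on the removed patient being one who had an event. 'About half' applies only when exactly two patients had events (1/24 divided by 2/25 is 0.52). The consequence is a descriptive rate that could be understated and that depends on which section is followed. It is not a false-positive problem, and nothing here shows an intention to exclude anyone.

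**What to change.** Make three changes in the SAP, before any data review:

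1. In 7.2, replace the strategy sentence with a fixed rule: no consented patient who received Praxbind, and no ADR or fatal AE, is removed from the primary or safety analysis because of a protocol violation, including categories added later. Violations are listed and counted only. Any analysis without violators is an additional sensitivity analysis and does not replace the full result.
2. In 7.3, define the Treated Set as all consented patients who received at least one dose, regardless of eligibility, so that it matches 8.8. Changing 7.2 alone would leave the contradiction in place.
3. Reconcile row A2.1 with the Screened Set. The row says a patient without consent is excluded from nothing, but such a patient cannot enter any set that starts from a signed consent form.

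The Treated Set would then no longer sit inside the Entered Set. Since Table 6.3: 1 puts baseline data on the Entered Set, baseline should also be shown for the Treated Set.

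The cost is two or three SAP sentences with that conforming table entry, and no new data. The sponsor gives up discretion that the table already disclaims, and the primary set may include a few patients outside the entry criteria, whom the violation listing would identify.
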